7.3.6.2 Etiologically Relevant Windows for Exposure Assessment

For most study outcomes, the analysis will include weekly exposure cohorts that are formed throughout pregnancy (i.e., approximately 40 potential weekly cohorts beginning at Week 2 through Week 40 or the latest observed week of gestation). However, analyses of spontaneous abortion and elective termination will be restricted to the Week 2-19 Cohorts, because spontaneous abortion is defined as a pregnancy loss occurring before 20 weeks' gestation, and all pregnancies that are ongoing at Week 20 will be censored in these analyses. Analyses of preterm birth will be restricted to Weeks 2-36 Cohorts, because preterm birth is defined as a livebirth occurring before 37 weeks' gestation, and analyses of ectopic pregnancy and MCMs will be restricted to Weeks 2-13 Cohorts.

Table 2 depicts the potential gestational weeks of cohort entry for each study outcome relative to the timing of outcome assessment.

Table 2 Etiologically relevant exposure windows for study outcomes

Study Outcome	Etiologically Relevant Exposure Window	Potential Cohort Entry of Pregnancy	Start of Follow-up¹	Censoring Events²
Ectopic pregnancy	First trimester	Week 2 – Week 13	Cohort entry	End of pregnancy, disenrollment from the health plan/8 weeks of no clinical activity, or the end of the study period
Elective termination	ECD through 19 weeks' gestation (19 weeks + 6 days)	Week 2 – Week 19	Cohort entry	20 weeks + 0 days, end of pregnancy, disenrollment from the health plan/8 weeks of no clinical activity, or the end of the study period
Live births	Entire pregnancy	Week 2 – Week 40	Later of cohort entry or 20 weeks + 0 days	End of pregnancy, disenrollment from the health plan/8 weeks of no clinical activity, or the end of the study period
Preterm birth	ECD through 36 weeks' gestation (36 weeks + 6 days)	Week 2 – Week 36	Later of cohort entry or 20 weeks + 0 days	37 weeks + 0 days, end of pregnancy, disenrollment from the health plan/8 weeks of no clinical activity, or the end of the study period

Study Outcome	Etiologically Relevant Exposure Window	Potential Cohort Entry of Pregnancy	Start of Follow-up ¹	Censoring Events ²
Spontaneous abortion	ECD through 19 weeks' gestation (19 weeks + 6 days)	Week 2 – Week 19	Cohort entry	20 weeks + 0 days, end of pregnancy, disenrollment from the health plan/8 weeks of no clinical activity, or the end of the study period

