7.4.2.1.4 Preterm Birth

Preterm birth is defined as a live birth occurring before the 37th week of pregnancy based on LMP. It will be identified on maternal records based on ICD-10-CM O60.1* diagnosis codes and on infant records based on ICD-10-CM P07.2* and P07.3* codes, as described in [Appendix E](#). Based on a validation study, a similar algorithm had a PPV of 92.3% (95% CI 82.1, 100.0; [Chomistek et al., 2023b](#)).

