Outcome	Type	Code(s)	Code Description
MCM	ICD-10-CM	Q67*	Congenital musculoskeletal deformities of head, face, spine and chest
MCM	ICD-10-CM	Q68*	Other congenital musculoskeletal deformities
MCM	ICD-10-CM	Q69*	Polydactyly
MCM	ICD-10-CM	Q70**	Syndactyly
MCM	ICD-10-CM	Q71***	Reduction defects of upper limb
MCM	ICD-10-CM	Q72***	Reduction defects of lower limb
MCM	ICD-10-CM	Q73*	Reduction defects of unspecified limb
MCM	ICD-10-CM	Q74*	Other congenital malformations of limb(s)
MCM	ICD-10-CM	Q75*	Other congenital malformations of skull and face bones
MCM	ICD-10-CM	Q76***	Congenital malformations of spine and bony thorax
MCM	ICD-10-CM	Q77*	Osteochondrodysplasia with defects of growth of tubular bones and spine
MCM	ICD-10-CM	Q78*	Other osteochondrodysplasias
MCM	ICD-10-CM	Q79**	Congenital malformations of musculoskeletal system, not elsewhere classified
MCM	ICD-10-CM	Q80*	Congenital ichthyosis
MCM	ICD-10-CM	Q81*	Epidermolysis bullosa
MCM	ICD-10-CM	Q82*	Other congenital malformations of skin
MCM	ICD-10-CM	Q83*	Congenital malformations of breast
MCM	ICD-10-CM	Q84*	Other congenital malformations of integument
MCM	ICD-10-CM	Q85**	Phakomatoses, not elsewhere classified
MCM	ICD-10-CM	Q86*	Congenital malformation syndromes due to known exogenous causes, not elsewhere classified
MCM	ICD-10-CM	Q87***	Other specified congenital malformation syndromes affecting multiple systems
MCM	ICD-10-CM	Q89**	Other congenital malformations, not elsewhere classified
Preterm birth	ICD-10-CM	O60.10**	Preterm labor with preterm delivery
Preterm birth	ICD-10-CM	O60.12**	Preterm labor second trimester with preterm delivery second trimester
Preterm birth	ICD-10-CM	O60.13**	Preterm labor second trimester with preterm delivery third trimester
Preterm birth	ICD-10-CM	O60.14**	Preterm labor third trimester with preterm delivery third trimester
Preterm birth	ICD-10-CM	P07.2*	Extreme immaturity of newborn
Preterm birth	ICD-10-CM	P07.3*	Preterm [premature] newborn [other]
SGA	ICD-10-CM	P05.0*	Newborn light for gestational age
SGA	ICD-10-CM	P05.1*	Newborn small for gestational age
Spontaneous abortion	ICD-10-CM	O02.1	Missed abortion
Spontaneous abortion	ICD-10-CM	O03**	Spontaneous abortion
Spontaneous abortion	CPT ⁷	01965	Anesthesia for incomplete or missed abortion procedures
Spontaneous abortion	CPT	59800	Treatment Of Spontaneous Abortion, First Trimester
Spontaneous abortion	CPT	59801	Treatment Of Spontaneous Abortion, First Trimester

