⁷ CPT copyright 2024 American Medical Association. All rights reserved.

Outcome	Type	Code(s)	Code Description
Spontaneous abortion	CPT ⁸	59810	Treatment Of Spontaneous Abortion, Second Trimester
Spontaneous abortion	CPT	59811	Treatment Of Spontaneous Abortion, Second Trimester
Stillbirth	ICD-10-CM	Z37.1	Single stillbirth
Stillbirth	ICD-10-CM	Z37.3	Twins, one liveborn and one stillborn
Stillbirth	ICD-10-CM	Z37.6*	Other multiple births, some liveborn
Stillbirth	ICD-10-CM	Z37.4	Twins, both stillborn
Stillbirth	ICD-10-CM	Z37.7	Other multiple births, all stillborn
Stillbirth	ICD-10-CM	O31.00	Papyraceous fetus, unspecified trimester
Stillbirth	ICD-10-CM	O31.02	Papyraceous fetus, second trimester
Stillbirth	ICD-10-CM	O3103X0	Papyraceous fetus, third trimester, not applicable or unsp
Stillbirth	ICD-10-CM	P95	Stillbirth
Stillbirth	ICD-10-CM	O36.4	Maternal care for intrauterine death

Abbreviations: CPT, Current Procedural Terminology codes; HICL, Hierarchical Ingredient Code List

ICD-10, International Classification of Diseases, 10th Revision;

ICD-10-CM, International Classification of Diseases, 10th Revision, Clinical Modification;

MCM, major congenital malformation; SGA, small for gestational age

Subcodes for minor congenital malformations will be removed from the definition of MCM.

* Indicates how many additional decimal places should be included in the wildcard for billable codes only.

⁸ CPT copyright 2024 American Medical Association. All rights reserved.

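### Preterm birth is defined as a live birth, but the maternal O60.1* codes that identify it show no vital status and are paired with no live-birth code, so a preterm stillbirth can be counted

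*Protocol*

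**What the plan says.** Section 7.4.2.1.4 gives the definition: "Preterm birth is defined as a live birth occurring before the 37th week of pregnancy based on LMP". Section 7.3.6.2 repeats it when setting the exposure window: "preterm birth is defined as a livebirth occurring before 37 weeks' gestation".

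Section 7.4.2.1.4 then gives the identification rule in two parts. For the mother: "It will be identified on maternal records based on ICD-10-CM O60.1* diagnosis codes". For the infant: "and on infant records based on ICD-10-CM P07.2* and P07.3* codes". It does not say whether both parts are needed or either will do.

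Appendix E lists the codes. All four O60.1 rows describe preterm labour with preterm delivery, for example "Preterm labor third trimester with preterm delivery third trimester". The P07 rows are newborn codes, for example "Extreme immaturity of newborn". Live-birth codes (Z37.0, Z37.2, Z37.3, Z37.5*, Z37.6*, Z38**) and stillbirth codes (for example Z37.1, "Single stillbirth") are in the same appendix, but the preterm birth rows are tied to neither set.

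In Table 2, preterm birth and stillbirth both start follow-up at the later of cohort entry and 20w+0d. Preterm follow-up stops at 37w+0d.

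**The concern.** The definition limits the outcome to live births, but the maternal code rule, as listed, does not carry that limit. A stillbirth delivered after preterm labour can carry an O60.1* code and stillbirth codes at the same delivery. It could then satisfy both outcome rules during the weeks in which both outcomes are followed.

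If that happens, preterm birth frequency is somewhat overstated. Part of any effect on stillbirth would also pass into the preterm birth hazard ratio. A pregnancy safety study reports these as separate outcomes so that they can be read separately.

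**Working it through.** **1. Definition against rule**

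| Item | Where | Live birth required? |
|---|---|---|
| Definition of preterm birth | 7.3.6.2, 7.4.2.1.4 | Yes |
| Maternal O60.1* codes | 7.4.2.1.4, Appendix E | Not in the code descriptions; no companion code |
| Infant P07.2*, P07.3* codes | 7.4.2.1.4, Appendix E | Newborn codes, on the infant's record |
| Check for other outcome codes on the same date | 7.4.2.1.6 (stillbirth) | One arm of an OR; the arm requiring at least two stillbirth codes qualifies without it |

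The stillbirth algorithm therefore does not stop the same delivery from also meeting the preterm rule. No order of precedence between the two outcomes is stated.

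**2. Are both records needed, or either?** Section 7.2.1.1 says about 85% of live-birth pregnancies can be linked to an infant, so about 100 - 85 = 15% cannot. Requiring both records would lose the preterm births in that 15%. Preterm birth is also listed among the pregnancy outcomes (7.4.2.1), while section 7.7.3.2 describes only the infant outcomes as necessarily restricted to linked infants. The either-record reading is therefore likelier, though the text does not settle it.

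**3. The plan's own figures.** Table 3 gives 115 / 57 / 34 exposed live births for preterm birth at RR 2 / 2.5 / 3. Inputs are 10% prevalence, 1:4 ratio, 80% power and two-sided 0.05. The Fleiss formula without continuity correction is

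n = [1.96·√((1+1/4)·p̄(1-p̄)) + 0.8416·√(p1(1-p1) + p2(1-p2)/4)]² / (p1-p2)²

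At RR 2: p1 = 0.20, p2 = 0.10, p̄ = (0.20 + 4·0.10)/5 = 0.12, and n = (0.712 + 0.360)²/0.01 = 114.8, so 115. RR 2.5 and 3 give 57 and 34. Dividing by 0.80 × 0.76 = 0.608 gives 189.1 / 93.8 / 55.9 pregnancies, against the stated 190 / 94 / 56. These figures reproduce and are not in dispute. They are already expressed in live births, so adding a live-birth condition does not change them.

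**4. Size of the possible leak.** Table 3 gives preterm birth 10% and stillbirth 1%. Let s be the share of stillbirths that are preterm and carry an O60.1 code. The documents do not give s, so 10%, 30% and 60% are assumptions. In percentage points, b = 1 × s.

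- Share of counted preterm births that are stillbirths = b/(10 + b)
- Apparent preterm RR when the true RR is 1 and the stillbirth RR is R = (10 + R·b)/(10 + b)

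| s | b | Share | R = 2 | R = 3 |
|---|---|---|---|---|
| 10% | 0.1 | 0.1/10.1 = 1.0% | 10.2/10.1 = 1.01 | 10.3/10.1 = 1.02 |
| 30% | 0.3 | 0.3/10.3 = 2.9% | 10.6/10.3 = 1.03 | 10.9/10.3 = 1.06 |
| 60% | 0.6 | 0.6/10.6 = 5.7% | 11.2/10.6 = 1.06 | 11.8/10.6 = 1.11 |

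With R = 1 and a true preterm RR of 1 there is no distortion.

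**5. Ceiling.** If every stillbirth were preterm and coded O60.1, the share would be 1/11 = 9.1%. If the 1% is instead rescaled to live births using Table 3's 76% (1/0.76 = 1.32), it would be 1.32/11.32 = 11.6%.

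**The case against.** A reader might infer that the plan counts preterm stillbirths as preterm births. The documents do not support that. No rule says so, the definition excludes them twice, and the identification sentence also names newborn codes on the infant record. If both records are required, a stillbirth coded only on the mother's record would not qualify. The supportable statement is that such a delivery can be counted on the likelier reading, not that it will be.

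Two further inferences should be set aside. The date of a preterm delivery is both an event date and the end of pregnancy, but this is true of every outcome that ends a pregnancy; it is ordinary notation and not a fault. Nor are stillbirth and live birth exclusive at pregnancy level: Appendix E lists Z37.3 and Z37.6* under both, since a multiple pregnancy can have both.

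It can also be said that precedence rules may sit in the SAP or in DAPI, the pregnancy-identification process. However, section 7.4.2 places the outcome code lists in this protocol, whereas exclusion and covariate lists are deferred to the SAP. DAPI is described only for the Optum Research Database, with no precedence rule shown, and other data sources are to be added.

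The protocol also cites validation: "a similar algorithm had a PPV of 92.3"%. That leaves 100 - 92.3 = 7.7% false positives, with no breakdown, for an algorithm that is similar and not stated to be identical. It neither shows nor rules out a leak of 1-6%. The bias analysis for differential outcome misclassification (7.7.3.5.7) could explore the effect afterwards but would not remove it.

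What stands of the objection is that the effect is small, the assumed share has no source in the documents, and this is not the primary outcome.

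**Conclusion.** The concern holds as a gap between definition and rule: the maternal codes as listed do not enforce the live-birth condition and can admit preterm stillbirths. This depends on a maternal O60.1* code being sufficient by itself, and on reading the O60.1 descriptions as Appendix E gives them.

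Under the assumed 10-60% share, about 1-6% of counted preterm births would be stillbirths. A null preterm RR would read 1.01-1.06 at a stillbirth RR of 2 and 1.02-1.11 at a stillbirth RR of 3, the largest RR in Table 3. The smallest preterm RR in Table 3 is 2, so the leak alone would not produce an effect of that size. It would also not make the two outcomes impossible to read apart: stillbirth is analysed separately, and on these assumptions 94-99% of counted preterm births are live births. No sample-size figure is affected. The change is worth making because it is cheap and brings the rule into line with the definition.

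**What to change.** In section 7.4.2.1.4 and the preterm birth rows of Appendix E:

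1. Count an O60.1* code as preterm birth only when the same delivery also has a live-birth code from the protocol's own list (Z37.0, Z37.2, Z37.3, Z37.5*, Z37.6* or Z38**) or a linked liveborn infant.
2. State that the maternal and infant codes are alternatives, so that preterm births without a linked infant are kept.
3. State that a delivery meeting the stillbirth rule with no liveborn infant ends preterm follow-up without an event. A multiple pregnancy with one liveborn and one stillborn infant may still count under both outcomes.

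The cost is one added condition using codes already in Appendix E. A few preterm live births with neither a live-birth code nor a linked infant would be missed.
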